9.4.6. Pharmacokinetic/Pharmacodynamic Analyses

The 'PK Population' is defined as subjects for whom a PK sample was obtained and analyzed. This will be the population used for all the PK displays.

The following plasma PK parameters will be determined for daprodustat and metabolites: C_{τ} (pre-dose) and C_{\max} .

Plasma daprodustat and metabolites concentration data will be listed and summarized by planned collection time and daprodustat dose administered at PK visit. PK parameter data will be listed and summarized by daprodustat dose administered at PK visit, and dose-normalized (per mg) PK parameter data will be summarized.

All PK data will be stored in the Archives, GlaxoSmithKline Pharmaceuticals, R&D.

The following exploratory graphics will be created. Based on these, and the efficacy and safety results from other Phase 3 studies, post-hoc exploratory exposure-response/safety modelling may be conducted, including exploratory graphics with metabolites. Further details will be provided in the RAP.

- Scatter plots of daprodustat PK parameters (C_{τ} and C_{\max}) dose normalized to 1 mg vs. percent time in range during EP.
- Scatter plots of average daprodustat dose during EP vs. percent time in range during EP.
- Scatter plots of daprodustat PK parameters (C_{τ} and C_{\max}) dose normalized to average dose during EP vs. percent time in range during EP.
- Scatter plots of daprodustat PK parameters (C_{τ} and C_{\max}) dose normalized to 1 mg vs. change from baseline of Hgb during EP.
- Scatter plots of average daprodustat dose during EP vs. change from baseline of Hgb during EP.
- Scatter plots of daprodustat PK parameters (C_{τ} and C_{\max}) dose normalized to average dose during EP vs. change from baseline of Hgb during EP.
- Boxplots of daprodustat PK parameters dose normalized to 1 mg by subjects with or without MACE or a combined safety endpoint of MACE + thromboembolic event + hospitalization for heart failure

- Boxplots of daprodustat PK parameters dose normalized to dose at time of MACE or combined safety endpoint (or end of treatment if no endpoint) by subjects with or without MACE or combined safety endpoint

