
 PK exploratory endpoints described as dose normalized 	
 PK exploratory endpoints described as dose extrapolated 	
 Terminology clarification following discussion with regulatory agencies.
PK exploratory endpoints include: 
 Scatter plots of daprodustat PK parameters (C_{tau} and C_{max}) dose normalized to 1 mg vs. 	PK exploratory endpoints modified as follows: 
 Endpoints removed: Scatter plots of daprodustat PK 	
 Removed as these endpoints do not provide additional information for efficacy explorations than

CONFIDENTIAL

201410

Protocol	Reporting & Analysis Plan	
Statistical Analysis Plan	Statistical Analysis Plan	Rationale for Changes

percent time in range during EP.
 
 Scatter plots of average daprodustat dose during EP vs. percent time in range during EP. Scatter plots of daprodustat PK parameters (C_{tau} and C_{max}) dose normalized to average dose during EP vs. percent time in range during EP. Scatter plots of daprodustat PK parameters (C_{tau} and C_{max}) dose normalized to 1 mg vs. change from baseline of Hgb during EP. Boxplots of daprodustat PK parameters (C_{tau} and C_{max}) dose normalized to 1 mg by subjects with or without MACE or combined safety endpoint 	
parameters (C_{tau} and C_{max}) dose normalized to 1 mg vs. percent time in range during EP.
 
 Scatter plots of average daprodustat dose during EP while in target Hgb range vs. percent time in range during EP. Scatter plots of daprodustat PK parameters (C_{tau} and C_{max}) dose normalized to average dose during EP while in target Hgb range vs. percent time in range during EP. Endpoints removed: Scatter plots of daprodustat PK parameters (C_{tau} and C_{max}) dose normalized to 1 mg vs. change from baseline of Hgb during EP. Endpoints removed: Boxplots of daprodustat PK parameters (C_{tau} and C_{max}) dose normalized to 1 mg by subjects with or without MACE or combined safety endpoint 	
what will be available from remaining endpoints.

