8.3.3. Pharmacokinetic Parameters**8.3.3.1. Deriving Pharmacokinetic Parameters**

- Refer to [Appendix 5: Data Display Standards & Handling Conventions \(Section 10.5.3 Reporting Process & Standards\)](#).
- The pharmacokinetic parameters of parent GSK1278863, and metabolites (GSK2391220 (M2), GSK2506104 (M3), and GSK2531401 (M13)) will be calculated by programming methods.

CONFIDENTIAL

201410

- All calculations of non-compartmental parameters will be based on actual sampling times.
- Pharmacokinetic parameters described in [Table 15](#) will be determined from the plasma concentration-time data, as data permits.

Table 15 Derived Pharmacokinetic Parameters for GSK1278863, and/or GSK2391220 (M2), GSK2506104 (M3) and GSK2531401 (M13)

Parameter	Parameter Description
GSK1278863, GSK2391220 (M2), GSK2506104 (M3) and GSK2531401 (M13)	
Tmax	Time to reach Cmax, determined directly from the concentration-time data.
Ctau	Observed concentration at dosing interval (tau=24 h, predose sample)
Cmax	Maximum observed concentration, determined directly from the concentration-time data.
GSK1278863	
Avg Dose during EP TIR	The average daily GSK1278863 dose when the subject is on-treatment and in target Hgb range during the evaluation period (EP) Weeks 28-52 (see Section 10.6.3.1). Evaluable Hgb values are used to determine time in range. Subjects who permanently stop randomized treatment before the beginning of the EP, and subjects who have 0% time in range (e.g., subjects who have an evaluable Hgb below or above range for the entire EP) will have a missing value for this parameter.
Avg Dose EP	The average daily GSK1278863 dose when the subject is on-treatment during the EP.
Dose at first MACE	The daily GSK1278863 dose at the time of the subject's first on-treatment adjudicated MACE. If the subject does not have an on-treatment adjudicated MACE, this value is missing.
Final Dose for Subjects without MACE	For subjects without an on-treatment adjudicated MACE, this is the subject's final GSK1278863 dose during the study.
Dose at first MACE++	The daily GSK1278863 dose at the time of the subject's first on-treatment adjudicated MACE++ (defined as the first adjudicated MACE, hospitalization for heart failure, or thromboembolic event) If the subject does not have an on-treatment adjudicated MACE++, this value is missing.
Final Dose for Subjects without MACE++	For subjects without an on-treatment adjudicated MACE++, this is the subject's final GSK1278863 dose during the study.

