Ctau/1mg Dose	Ctau extrapolated to 1mg dose: Observed Ctau divided by dose administered on the PK day
Ctau/Avg Dose EP TIR	Ctau extrapolated to average dose during EP TIR: Ctau/1mg multiplied by the average daily GSK1278863 dose when the subject is on-treatment and in target Hgb range during Weeks 28-52 (see Section 10.6.3.1). Evaluable Hgb values are used to determine time in range.
Ctau/Avg Dose EP	Ctau extrapolated to average dose during EP: Ctau/1mg multiplied by the average daily GSK1278863 dose during the EP.

CONFIDENTIAL

201410

Parameter	Parameter Description
Ctau/Dose at first MACE	Ctau extrapolated to dose at first on-treatment adjudicated MACE: Ctau/1mg multiplied by the daily GSK1278863 dose at the time of the subject's first on-treatment adjudicated MACE.
Ctau/Final Dose for subjects without MACE	For subjects without an on-treatment adjudicated MACE, this is the subject's Ctau/1mg multiplied by the subject's final daily GSK1278863 dose during the study.
Ctau/Dose at first MACE++	Ctau extrapolated to dose at first on-treatment adjudicated MACE++: Ctau/1mg multiplied by the daily GSK1278863 dose at the time of the subject's first on-treatment adjudicated MACE++.
Ctau/Final Dose for subjects without MACE++	For subjects without an on-treatment adjudicated MACE++, this is the subject's Ctau/1mg multiplied by the subject's final daily GSK1278863 dose during the study.
Cmax/1mg Dose	Cmax extrapolated to 1mg dose: Observed Cmax divided by dose administered on the PK day
Cmax/Avg Dose EP TIR	Cmax extrapolated to average dose during EP TIR: Cmax/1mg multiplied by the average daily GSK1278863 dose when the subject is on-treatment and in target Hgb range during Weeks 28-52 (see Section 10.6.3.1). Evaluable Hgb values are used to determine time in range.
Cmax/Avg Dose EP	Cmax extrapolated to average dose during EP: Cmax/1mg multiplied by the average daily GSK1278863 dose during the EP.
Cmax/Dose at first MACE	Cmax extrapolated to dose at MACE: Cmax/1mg multiplied by the daily GSK1278863 dose at the time of the subject's first on-treatment adjudicated MACE.
Cmax/Final Dose for subjects without MACE	For subjects without an on-treatment adjudicated MACE, this is the subject's Cmax/1mg multiplied by the subject's final daily GSK1278863 dose during the study.
Cmax/Dose at first MACE++	Cmax extrapolated to dose at MACE++: Cmax/1mg multiplied by the daily GSK1278863 dose at the time of the subject's first on-treatment adjudicated MACE++.

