8.4. Pharmacokinetic / Pharmacodynamic Analyses

- The primary goal of this analysis is to characterize the pharmacokinetic/pharmacodynamic relationship of parent GSK1278863 and efficacy and safety endpoints in the “Pharmacokinetic” population from this study.
 - The influence of subject demographics and baseline characteristics, including disease activity in this population may be investigated.

CONFIDENTIAL

201410

- A summary of the planned population pharmacokinetic/pharmacodynamic analyses are outlined below:
 - Relationships between drug exposure and selected efficacy, MACE and MACE ++ events will be explored and characterized as data permit. The exposure will be estimated on the sparse PK collected in a sub-set of the study population. The data may be dose- extrapolated to the dose administered during the PK collection period. Any changes to the proposed analyses would be described in the CSR.

Table 16 Overview of Planned Pharmacokinetic / Pharmacodynamic Analyses for GSK1278863

Parameter	Untransformed						Log-Transformed							
	Stats Analysis			Summary		Individual		Stats Analysis			Summary		Individual	
	T	F	L	T	F	F	L	T	F	L	T	F	F	L
GSK1278863														
Scatter plot of % Time Evaluable Hgb in Range during EP vs. Avg Dose EP TIR						Y								
Scatter plot of Evaluable Hgb Change from Baseline during EP vs. Avg Dose EP						Y								
Scatter plot of % Time Evaluable Hgb in Range during EP vs. Ctau/Avg Dose EP TIR						Y								
Scatter plot of Evaluable Hgb Change from Baseline during EP vs. Ctau/Avg Dose EP						Y								
Boxplot of Ctau/Dose at On-treatment MACE or MACE++ by Subjects with or without On-treatment MACE or MACE++						Y								
Scatter plot of % Time Evaluable Hgb in Range during EP vs. Cmax/Avg Dose EP TIR						Y								
Scatter plot of Evaluable Hgb Change from Baseline during EP vs. Cmax/Avg Dose EP						Y								
Boxplot of Cmax/Dose at On-treatment MACE or MACE++ by Subjects with or without On-treatment MACE or MACE++						Y								

NOTES :

- T = Table, F = Figure, L = Listings, Y = Display generated.
- Stats Analysis = Represents TFL related to any formal statistical analyses (i.e. modelling) conducted.
- Summary = Represents TFL related to any summaries (i.e. descriptive statistics) of the observed raw data.
- Individual = Represents FL related to any displays of individual subject observed raw data.

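### The three percent-time-in-range plots in SAP Table 16 use an in-range dose that is missing at 0% time in range, so every subject with an outcome of 0% is left out of them

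*SAP*

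**What the plan says.** Protocol Section 9.4.6 plans "Scatter plots of average daprodustat dose during EP vs. percent time in range during EP", with Ctau and Cmax scaled to the same whole-period average dose. SAP Section 2.1, Table 1, changes both. The dose plot becomes "Scatter plots of average daprodustat dose during EP while in target Hgb range vs. percent time in range during EP", and the PK parameters become "dose normalized to average dose during EP while in target Hgb range vs. percent time in range during EP".

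SAP Section 8.3.3.1, Table 15, defines the new dose variable (Avg Dose during EP TIR) as "The average daily GSK1278863 dose when the subject is on-treatment and in target Hgb range during the evaluation period (EP) Weeks 28-52". It gives no value to anyone whose treatment ends before the evaluation period (EP) starts. The same rule is applied to "subjects who have 0% time in range (e.g., subjects who have an evaluable Hgb below or above range for the entire EP"): in the SAP's terms, each of them "will have a missing value for this parameter". The exposure variable is built from that dose: "Ctau/1mg multiplied by the average daily GSK1278863 dose when the subject is on-treatment and in target Hgb range". Cmax is built the same way.

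SAP Section 8.4, Table 16, then lists "Scatter plot of % Time Evaluable Hgb in Range during EP vs. Avg Dose EP TIR" and its Ctau and Cmax counterparts. These are the only time-in-range plots in that table. SAP Section 2.2 still lists the whole-EP plots and the plots normalized to 1 mg.

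**The concern.** A scatter plot of outcome against dose should be able to show a subject for whom treatment never achieved the outcome. Here the x-variable does not exist when the outcome is zero, so the plotted sample is selected on the outcome. For subjects who remain, doses taken while out of range are discarded, and the averaging window shrinks as the outcome worsens.

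Percent time in range is a secondary endpoint with its own non-inferiority margin, and these plots are how the plan relates dose and exposure to it. A reader would see a cloud of points with its floor removed and no indication of how many points are absent.

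The only rationale in that row of Table 1 concerns the plots that were removed, on the ground that the remaining ones carry the same information. It gives no reason for the switch to in-range dose. For time in range the ground also fails: the removed 1 mg plot would have kept PK-sampled subjects at 0%, and none of the remaining time-in-range plots does.

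**Working it through.** The plan states no figure to reproduce. The main check is definitional.

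1. **Outcome.** SAP Section 10.6.3.1 defines percent time in range (10 to 11.5 g/dL) for subjects whose treatment stop date is on or after Week 28 and who have at least two suitably timed evaluable Hgb values. It does not exclude 0%. A subject below or above range throughout has a valid y-value of 0.
2. **X-variable.** Table 15 makes in-range dose missing at 0%. I read its target range as 10 to 11.5 g/dL, because it refers to Section 10.6.3.1.
3. **Exposure.** Ctau or Cmax per 1 mg, multiplied by a missing dose, is missing.
4. **Result.** All subjects with a defined outcome of 0% are lost from all three plots. Subjects who stop before Week 28 have no outcome under either version, so the change does not affect them.
5. **Window.** Weeks 28 to 52 are 24 × 7 = 168 days. At 5% time in range, the dose is averaged over 0.05 × 168 = 8.4 days.
6. **Alternative.** Avg Dose EP in Table 15 requires only that the subject is on treatment in the EP. It exists for a subject at 0%, as do Ctau and Cmax scaled to it where a PK sample exists.

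**How many subjects?** The documents do not say. As an illustration, assume seven EP Hgb values joined linearly, mean 10.5 g/dL, between-subject SD 0.5 to 1.0 and within-subject SD 0.3 to 0.8. The simulated share at 0% runs from 1.2% (SDs 0.5 and 0.8) to 26.6% (SDs 1.0 and 0.3). Mean time in range among plotted subjects is the overall mean divided by (1 − share at 0%):

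- 61.9% / (1 − 0.012) = 62.7%, about 1 percentage point too high.
- 52.4% / (1 − 0.266) = 71.4%, 19 percentage points too high.

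**Which direction?** Second illustration: 105 subjects, dose lognormal (median 6 mg, log SD 0.7, limited to 1 to 24 mg), time in range Beta(2, 1.6) and independent of dose. A share is then set to 0% and placed at chosen doses. Rank correlation of dose with time in range, all subjects kept:

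| 0% subjects placed at | 3% at zero | 5% at zero | 10% at zero |
|---|---|---|---|
| 12, 16 or 24 mg | −0.07 | −0.12 | −0.22 |
| half high, half 1 to 4 mg | within 0.03 of zero | within 0.03 of zero | within 0.03 of zero |
| 1 to 4 mg | +0.07 | +0.10 | +0.20 |

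I re-ran this; the first and third rows agree to about 0.01. Once the 0% subjects are dropped, every cell is 0.00. That zero is built in, because dose and time in range were generated independently. What the table shows is that the sign of what is hidden depends on where the 0% subjects sit. Mean time in range at 12 mg or more, with all subjects kept, is 47%, 42% and 33% in the first row and about 56% in the third. It is about 56% in every case once they are dropped.

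**The case against.** Four points have force.

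**The loss is confined.** Table 16 also plots evaluable Hgb change against whole-EP dose, Ctau and Cmax, and those plots keep subjects at 0%. The secondary analysis of percent time in range keeps them as well, and whole-EP dose is summarized and listed. A reader might infer that every complete failure vanishes from the exposure-response work. The documents do not support that; only the three time-in-range plots are affected.

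**The direction is not determined.** A reader might infer that high dose will look more effective than it was. That holds only if the omitted subjects sit at high doses. Subjects above range throughout are also at 0%, and the dose adjustment scheme in Protocol Appendix 3 steps their dose down or holds it, so they would tend to sit low. The table shows the sign reversing.

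**Whole-EP dose is not the truth either.** Dose is titrated to Hgb, so poor responders are escalated. A negative whole-EP correlation would partly show titration. In-range dose describes something different, the dose held while in range, and has some descriptive use. But the SAP does not offer this as its reason, selecting on the outcome does not remove the confounding, and the SAP itself uses whole-EP dose for the Hgb-change plots.

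**105 is the wrong denominator.** It is the protocol's evaluable number per arm at 30% non-evaluable. SAP Section 8.4 uses the PK population, and Protocol Section 7.5 samples in-center hemodialysis subjects in the daprodustat arm, so fewer points will be plotted.

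The definitional point survives all four.

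**Conclusion.** The point holds for the three time-in-range plots and rests on the SAP's own definitions. Every subject with a defined outcome of 0% is omitted, and for the rest the x-value is averaged over a window set by the outcome. The displayed relationship can be distorted either way.

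The number omitted is unknown. The 1% to 27% range and the correlations are illustrations under the stated assumptions, not predictions for this trial.

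The consequence is limited. SAP Section 2.2 classes these as exploratory displays with no statistical testing planned, and no primary or principal secondary result depends on them. A reader might infer that the efficacy conclusions are biased; nothing in the documents supports that. The change is still worth making: the switch is unexplained, and Section 2.2 conflicts with Tables 1 and 16, so the SAP needs an edit in any case.

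**What to change.** - In SAP Tables 1 and 16, plot percent time in range against Avg Dose EP, Ctau/Avg Dose EP and Cmax/Avg Dose EP, as the protocol planned. Table 15 already derives all three.
- If the in-range-dose plots are wanted, keep them as additional displays, state the reason for them in Table 1, and footnote the number of 0% subjects omitted.
- Align the endpoint list in SAP Section 2.2 with Tables 1 and 16, including the 1 mg versions that Table 1 removes.
- Note on the plots that dose is titrated to Hgb, so neither version shows a causal dose-response.

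The cost is a little more SAP text and, if both versions are kept, three more figures. No new variable or data collection is needed.

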2.2. Study Objective(s) and Endpoint(s)

Objectives	Endpoints
Primary Objectives	Primary Endpoints

 To compare daprodustat to rhEPO for Hgb efficacy (non-inferiority) 	
 Mean change in Hgb between baseline and evaluation period (EP, mean over Weeks 28-52)
Principal Secondary Objectives	Principal Secondary Endpoints (tested for superiority, adjusted for multiplicity)

 To compare daprodustat to rhEPO on the use of intravenous (IV) iron 	
 Average monthly IV iron dose (mg)/subject from baseline to Week 52
Secondary Objectives	Secondary Endpoints (tested for superiority¹, no multiplicity adjustment)

 To compare daprodustat to rhEPO on BP 	
 Change from baseline in SBP, DBP, and MAP at Week 52 and at end of treatment

CONFIDENTIAL

201410

Objectives	Endpoints
	
 Number of BP exacerbation events per 100 patient years N (%) with at least one BP exacerbation event during study

 To compare daprodustat to rhEPO on Hgb variability 	
 Hgb change from baseline to Week 52¹ N (%) responders, defined as mean Hgb within the Hgb analysis range 10-11.5 g/dL during the EP (Weeks 28 to 52) % time Hgb in analysis range 10-11.5 g/d during the EP (non-inferiority analysis that will use a margin of 15% less time in range)¹

 To compare daprodustat to rhEPO on the time to rescue (defined as permanently stopping randomized treatment due to meeting rescue criteria) 	
 Time to stopping randomized treatment due to meeting rescue criteria

 To compare daprodustat to rhEPO on HRQoL and Utility score 	
 Mean change in SF-36 HRQOL scores (PCS, MCS and 8 health domains) between baseline and Weeks 8, 12, 28, 52, of particular interest are the changes from baseline in the vitality and physical functioning domains at Weeks 28 and 52 Change from baseline in Health Utility (EQ-5D-5L) score at Week 52 Change from baseline in EQVAS at Week 52

 To compare daprodustat to rhEPO on the symptom severity and change 	
 Change from Baseline at Wk 52 by domain and overall symptom score on the CKD-AQ Change from Baseline at Wk 8,12, 28, 52 in PGI-S

 To summarize the PK parameters of daprodustat and three major metabolites in dialysis subjects 	
 Plasma daprodustat, M2, M3, and M13 PK parameters pre-dose trough (Ctau) and Cmax
Exploratory Objectives	Exploratory Endpoints (Statistical testing not planned)

 To further compare daprodustat and rhEPO on Hgb variability 	
 Hgb observed and change from baseline across all visits to end of treatment % of time Hgb is above, within and below the analysis range (10-11.5 g/dL) during EP Number (%) of subjects with mean Hgb above, within and below the Hgb analysis range during EP and at the end of treatment Number (%) of subjects with a Hgb <7.5 g/dL during the EP Number of times Hgb <7.5 g/dL during the EP Number (%) of subjects with a >1 g/dL increase in Hgb over 2 weeks (assessed at Week 2 and Week 4) or a >2 g/dL increase in Hgb within any 4-week period from Week 4 to Week 52 Number (%) of subjects with a >1 g/dL decrease in Hgb over 2 weeks (assessed at Week 2 and Week 4) or a >2 g/dL decrease in Hgb within any 4-week period from Week 4 to Week 52 N (%) of subjects with a Hgb value \geq 12 g/dL during the EP Number of times Hgb \geq 12 g/dL during the EP % of time Hgb \geq12 g/dL during the EP

CONFIDENTIAL

201410

Objectives	Endpoints

 To compare daprodustat to rhEPO on measures of iron parameters 	
 Observed and change from baseline in hepcidin, ferritin, transferrin saturation, total iron, total iron binding capacity (TIBC) across all visits to end of treatment Average quarterly TSAT Average quarterly ferritin Average quarterly IV iron dose/subject N (%) of subject who met iron management criteria

 To compare daprodustat to rhEPO on the need for RBC and whole blood transfusions 	
 Number (%) of subjects who receive at least one RBC or whole blood transfusion by Week 52 Number of RBC and whole blood transfusions per 100 patient years Number of RBC and whole blood units per 100 patient years

 To evaluate the dose adjustment schemes 	
 Assigned dose by visit and at Day 1, Week 28, Week 52 Most recent dose prior to Week 28, Week 52 Number (%) of subjects with 0, 1, 2 or >2 dose adjustments during the following periods: 
 Day 1 - < Week 28 Week 28 - < Week 52 Day 1 - < Week 52 Number of dose adjustments during the following periods: 
 Day 1 - < Week 28 Week 28 - < Week 52 Day 1 - < Week 52 Time dose held for Hgb \geq12 g/dL

 To further compare daprodustat to rhEPO on BP and BP medication changes 	
 Observed and change from baseline in SBP, DBP and MAP by visit Number of BP medications per subject by visit Change from baseline in the number of BP medications per subject by visit N (%) of subjects who had no change, an increase or a decrease in the dosage or number of BP medications from baseline by visit

 To compare daprodustat to rhEPO on lipid parameters 	
 Observed and % change from baseline in lipid parameters by visit [total cholesterol, direct low density lipoprotein cholesterol (LDL-C), high density lipoprotein cholesterol (HDL-C)]

 To further compare daprodustat to rhEPO on the symptom severity and change 	
 Change from Baseline at Wk 8,12, 28, & 52, by item on the CKD-AQ Shift tables (Baseline to Wk 8, 12, 28, & 52) in PGI-S N (%) of subjects within each PGI-C symptom change level at Wk 8, 12, 28, 52.

 To further compare daprodustat to darbepoetin alfa on HRQoL and Utility score 	
 Change from baseline in Health Utility (EQ-5D-5L) score at Weeks 8,12, & 28 Change from baseline in EQ VAS at Weeks 8, 12, & 28

 To evaluate graphical relationships between exposure parameters and selected efficacy endpoints 	
 Scatter plots of daprodustat PK parameters (Ctau and Cmax) dose normalized to 1 mg vs. percent time in range during EP.

CONFIDENTIAL

201410

Objectives	Endpoints
	
 • Scatter plots of average daprodustat dose during EP vs. percent time in range during EP. • Scatter plots of daprodustat PK parameters (Ctau and Cmax) dose normalized to average dose during EP vs. percent time in range during EP. • Scatter plots of daprodustat PK parameters (Ctau and Cmax) dose normalized to 1 mg vs. change from baseline of Hgb during EP. • Scatter plots of average daprodustat dose during EP vs. change from baseline of Hgb during EP. • Scatter plots of daprodustat PK parameters (Ctau and Cmax) dose normalized to average dose during EP vs. change from baseline of Hgb during EP.

 • To evaluate graphical relationships between daprodustat exposure and MACE and the composite endpoint of MACE + thromboembolic event + hospitalization for heart failure 	
 • Boxplots of daprodustat PK parameters (Ctau and Cmax) dose normalized to 1 mg by subjects with or without MACE or combined safety endpoint. • Boxplots of daprodustat PK parameters (Ctau and Cmax) dose normalized to dose at time of MACE or combined safety endpoint (or end of treatment if no endpoint) by subjects with or without MACE or combined safety endpoint.
Safety Objective	Safety Endpoints

 • To compare the safety and tolerability of daprodustat to rhEPO 	
 • Incidence and severity of AEs and SAEs including those special interest • Reasons for discontinuation of randomized treatment • Absolute values and changes from baseline in laboratory parameters, BP and heart rate (HR)

1. Hgb change from baseline to Wk 52 is tested for non-inferiority, using the -0.75 g/dL margin used in the primary analysis. % time in range is tested first for non-inferiority, then for superiority.

